## **Abstract**

Patients undergoing major head and neck surgery, especially those receiving a tracheostomy, are at risk for postoperative pulmonary complications. This is attributed to high prevalence of preexisting comorbidities in this population due to smoking, as well as the prolonged anesthesia time for these complex surgeries followed by prolonged periods of immobilization during recovery. Current oxygen therapy relies on cool mist delivered via a tracheostomy collar, which has been shown to be suboptimal as the airway functions best at physiological temperatures with a higher relative humidity than the aerosol mask can deliver. High flow humidified air is a safe and effective way to provide respiratory support, but has not been widely utilized after major head and neck surgery to prevent pulmonary complications. The goal of this randomized clinical trial is to evaluate the effectiveness of high flow oxygen at preventing postoperative pulmonary complications after major head and neck surgery, when compared to conventional oxygen therapy.

## **Background:**

Major head and neck surgery can come with considerable postoperative risk due to prolonged surgical procedures and time under anesthesia, that often directly involve the airway. Postoperative pulmonary complications are quite common after major head and neck surgery, estimated to be around 18.8-47%, and are increased in those requiring tracheostomy [1-5]. Head and neck oncology surgical patients are at high risk due to the high prevalence of preexisting cardiopulmonary disease, further complicated by a higher proportion of smokers [6]. The patients then undergo long surgeries with general anesthesia, often followed by prolonged immobilization during their recovery. The majority of these patients also undergo elective tracheostomy for airway protection. The tracheostomy can further increase risk for pulmonary complications, because it naturally bypasses the airways natural physiologic warming and humidification system. This causes pathological changes in the lower airways, including damage to the ciliated tracheal mucosa, thickening of airway secretions, and loss or reduction of mucociliary transport [7]. All of

NCT05362526  
IRB202102700  
9/22/22

these pathological changes can lead to pneumonia. While not often fatal in this population, pneumonia can still result in prolonged length of stay, need for intensive critical care, increased use of broad-spectrum antibiotics, and lengthen the time to tracheostomy decannulation [4].

The current standard for oxygen and humidification postoperatively is delivered via cool mist from an aerosol tracheostomy collar. Studies have shown this system is inadequate, as humidification delivered at room air causes mucociliary damage, resulting in increased airway secretion production and retention. Ultimately, this can cause serious complications like mucous plugging and pneumonia [8].

High flow oxygen therapy (HFOT) delivers heated and humidified oxygen, which has been shown to have multiple benefits, the first being able to delivery physiologically optimal heated humidification, as well as the ability to deliver positive airway pressure. By mimicking the optimal airway temperature and humidification, patients have less respiratory secretions and have improved clearance, preventing infection [9,10]. Positive airway pressure has been shown to improve oxygenation via increased end-expiratory lung volumes, and is important postoperatively as it can reduce lower airway collapse and atelectasis [11]. Meta-analysis of clinical trials, examining prophylactic use of HFOT during the immediate postoperative course for other major operations (cardiac, intrathoracic, abdominal), and showed a reduction in reintubation and the need to escalate respiratory support, when compared to conventional oxygen therapy [13].

Use of high flow after major head and neck surgery is generally unexplored. To date, only one study evaluates use of prophylactic HFOT tracheostomy collar after major head and neck surgery. In this small controlled trial (n=20), they concluded that HFOT was safe and feasible for this patient population [2].

### **Research Question**

Among subjects undergoing major head and neck surgery with tracheostomy, does perioperative use of HFOT tracheostomy collar, when compared to conventional oxygen therapy, result in fewer postoperative pulmonary complications?

### **Specific Aims**

1. Determine if HFOT tracheostomy is superior to conventional oxygen therapy at preventing postoperative complications
  - a. Determine the association between HFOT tracheostomy collar and postoperative pulmonary complications
  - b. Determine the association between HFOT tracheostomy collar and time to tracheostomy decannulation
  - c. Determine the association between HFOT tracheostomy collar and total length of stay after surgery

### **Research Plan**

#### **Study Design**

- Single center, non-blinded, prospective randomized clinical trial

Population:

- Inclusion
  - Patients undergoing major head and neck surgery that includes any neck dissection
    - Major head and neck surgery is defined as having a mean length of stay of three or more days, based on the diagnosis [14]
  - Surgery requires an elective tracheostomy for airway protection or laryngectomy tube in the case of total laryngectomy
- Exclusion
  - <18 years of age

## **Study Protocol**

### Screening

- Potential participants will be screened for enrollment at their preoperative surgery clinic appointments by their surgeon according to established inclusion/exclusion criteria. If the patient meets inclusion criteria, they will be referred to research coordinator to determine if patients wishes to participate and to consent the patient in person or via phone (see phone script for informed consent).
  - The following procedures will be performed during pre-operative consultation by one of the study team physicians.
  - Patient screening using predefined inclusion and exclusion criteria
  - Demographics, medical and medication history
  - Physical exam
  - Vital signs
  - Preoperative imaging is standard of care and ordered on all subjects prior to surgery
  - Subjects will be sent for pre-anesthesia testing for evaluation prior to surgery
    - At this appointment everyone will undergo EKG, chest radiograph, basic metabolic panel, complete blood count
    - This appointment must occur within 1 week from surgery
  - All patients are routinely presented at the University of Florida Jacksonville Head and Neck Tumor Board for discussion of diagnosis and ideal treatment
- Consent
  - Once subjects are determined eligible by the physician, they will be referred to the study coordinator. The study coordinator will meet the patient in person at the clinic or over the phone to discuss the full study details, and details of the study consent, including risks and benefits (see recruitment and consent scripts).

- This is so the patients will have time to adequately decide if they would like to participate in the study.
- If the patient chooses to not participate in the study, they will still receive conventional oxygen therapy.
- If the patient requests to speak to the treating surgeons about the study, they will be contacted separately to discuss the study as well as risks vs benefits.
- Informed consent will be obtained from the patient in person at a pre-operative clinic appointment, by phone/electronically via REDcap or on the day of surgery by the surgeon/resident or trained research coordinator, explaining risks and benefits of the study.
  - A written consent form will be presented to the patient with oral explanation from the research staff trained for formal study consent.
  - Patients will have opportunity to ask questions regarding the study and any risks that may be involved.

#### Randomization

- Randomization will be assigned by the study coordinator once the patient completes the consent process.
- Patients will be divided into three subgroups after enrollment: no free flap, free flap, and laryngo-pharyngectomy
- Randomization into COT vs HFOT will be performed based on a block randomization scheme, stratified by subgroup- no free flap, free flap, or laryngo-pharyngectomy.
- This system will be used to ensure well-balanced distribution into these three subgroups and in the two arms.
- The goal will be to always keep enrollment balanced accordingly to the usual volume of no free flap, free flap, or laryngo-pharyngectomy among the two treatment groups.
- The block randomization scheme will be generated by the analyst with the Center for Data Solutions at the UF College of Medicine Jacksonville, FL and it will be uploaded into REDCap before the data collection.

NCT05362526

IRB202102700

9/22/22

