### Day of Surgery

- If patients missed their preoperative labs and x-rays, the chest x-ray and labs can be drawn in the preoperative area the day of surgery
- The consents for surgery and the study will be completed
  - Subjects are allowed to drop from the study at any time. If they do, they will be treated with COT, which is our current standard of care

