### Operating Room

- In the operating room, patients will undergo their surgery per normal operating protocol. No patients will be treated differently because of the study.
- At the end of the procedure all patients requiring tracheostomy will have a size 8-0 cuffed Portex trach placed, the cuff will be deflated within 3 hours of leaving the operating room. Total laryngectomy patients will have a laryngectomy tube placed at end of procedure.
- The Anesthesia team will be instructed to treat the patients according to their normal standard of care for head and neck surgery
- All patients must be extubated prior to leaving the operating room, or else they will be dropped from the study
- Subjects will leave the operating room and be transported to the post anesthesia care unit for appropriate monitoring prior to being transferred to a progressive floor
- Starting at the PACU, tracheostomy patients will be started on COT or HFOT via tracheostomy adapter , until occlusive capping of the tracheostomy is tolerated. Once the trach is capped, patients can be placed on oxygen via nasal cannula if it is required to maintain O2 saturation levels as stated below.. Total laryngectomy patients will remain on COT or HFOT via trach mask adapter from the time they are in PACU until the time they can tolerate HME (heat moisture exchange) use or are discharged from the hospital, whichever comes first.

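### The arm is assigned at consent, before surgery, although it is first used in PACU; the operation and the extubation condition that drops patients therefore fall between allocation and treatment, with the operating team able to know the arm

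*Combined protocol and SAP*

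**What the plan says.** The trial is described under Study Design as "Single center, non-blinded, prospective randomized clinical trial". On allocation, the Randomization section says: "Randomization will be assigned by the study coordinator once the patient completes the consent process". The list is stratified by no free flap, free flap or laryngo-pharyngectomy and is loaded into REDCap before data collection.

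The Screening section allows consent in person at a pre-operative clinic visit, or "by phone/electronically via REDcap or on the day of surgery by the surgeon/resident or trained research coordinator". Under Day of Surgery, ahead of the operating-room steps, the protocol says: "The consents for surgery and the study will be completed".

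The assigned treatment begins after the operation: "Starting at the PACU, tracheostomy patients will be started on COT or HFOT via tracheostomy adapter". Laryngectomy patients also begin in PACU. Before that comes a condition on staying in the trial: "All patients must be extubated prior to leaving the operating room, or else they will be dropped from the study". The list of reasons for withdrawal repeats inability to be extubated in the operating room.

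Two sentences under Operating Room bear on intra-operative care. One reads: "No patients will be treated differently because of the study". The other instructs the anaesthesia team to follow its usual standard of care for this surgery.

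**The concern.** The arm is fixed before surgery but has no use until PACU. In an open-label trial, that leaves the whole operation in a period when the surgeon and anaesthesia team can know the arm. The surgeon or resident may even take the consent that triggers allocation.

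Two things are at stake. The firmer is the extubation condition. It is a judgement made in the operating room, after randomisation and before any assigned treatment, and failing it removes the patient. If knowledge of the arm influenced that judgement, the arms would lose different kinds of patients. The Statistical Analysis section defines no analysis population that would keep them in.

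The less firm is intra-operative care itself, such as ventilation, fluids and waking. If it shifted with the arm, it could affect early pulmonary outcomes, including atelectasis, which is a primary component. Analysing all randomised patients would not undo such a shift; only timing or concealment can prevent it.

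**Working it through.** **1. Order of events.**

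| Step | Where stated | Relation to surgery |
|---|---|---|
| Consent | Screening; Day of Surgery | Before, on every permitted route |
| Arm assigned | Randomization | On completion of consent, so before |
| Operation and anaesthesia | Operating Room | After allocation |
| Extubation condition; failure means dropped | Operating Room; withdrawal list | After allocation, before treatment |
| COT or HFOT starts | Operating Room | PACU, after surgery |

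Day-of-surgery consent shortens the gap but does not change the order.

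**2. Is the arm withheld in the gap?** No section says so. The two instructions under Operating Room ask for usual care; they do not conceal the arm. Nor does any section say that the team is told the arm. The supported statement is that the team is able to know it.

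**3. The plan's own sample size.** The inputs in the Statistical Analysis section are 30% and 10%, two-sided 5% significance and 90% power. With pooled variance and a mean proportion of 0.20:

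n = [1.960 × √(2 × 0.20 × 0.80) + 1.282 × √(0.30 × 0.70 + 0.10 × 0.90)]² / 0.20² = 82 per arm.

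This reproduces the stated 82. Moving the time of allocation does not change it. What changes is the meaning of the step from 82 to 91 per arm, which rests on 10% withdrawal. Patients who fail the operating-room condition now count as withdrawals after randomisation; under late allocation they would not.

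**4. Illustration of selective drops.** These assumptions are not in the documents: no true effect, 30% risk in both arms, no drops in control, and a fraction d of HFOT patients dropped whose risk is r times 30%. The observed HFOT risk is then

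(0.30 − d × r × 0.30) / (1 − d).

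| d | r | Observed HFOT risk | Spurious benefit (points) |
|---|---|---|---|
| 5% | 1.5 | (0.30 − 0.0225)/0.95 = 29.2% | 0.8 |
| 10% | 1.5 | (0.30 − 0.045)/0.90 = 28.3% | 1.7 |
| 10% | 2.0 | (0.30 − 0.060)/0.90 = 26.7% | 3.3 |
| 20% | 2.0 | (0.30 − 0.120)/0.80 = 22.5% | 7.5 |

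The design difference is 20 points. The table covers only the drop route and puts every drop in one arm; drops concentrated in control would reverse the sign. It says nothing about the size of any shift in intra-operative care.

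**The case against.** The strongest reply is that the harm is inferred. The coordinator assigns the arm, no section discloses it to the operating team, and both surgery and anaesthesia are told to proceed as usual. The anaesthesia instruction bears directly on ventilation, fluids and waking. This stands in part: the documents do not show that care would differ. But an instruction to follow usual practice still leaves room for individual judgement, and here the arm could be concealed without affecting treatment.

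A second reply is that staff know the arm throughout postoperative care, so concealment during surgery closes only a small part of the open-label exposure. That is true, and it limits the gain. It does not apply to the extubation condition, which is over before PACU.

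A reader might also infer more than the documents support:

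- *That the arm could steer the choice of airway or flap.* A tracheostomy or laryngectomy tube is an inclusion criterion, the tracheostomy type is fixed for all tracheostomy patients, and free-flap status is a stratum.
- *That the pre-operative film and laboratory tests are compromised.* The primary outcome uses postoperative radiographs, and the analysis gives the pre-operative film no role.
- *That a change of operation puts a patient in the wrong stratum and biases the result.* Stratifying on the planned operation is legitimate. A later change may weaken balance on the procedure performed, but it does not bias the randomised comparison.
- *That a failed extubation adds a primary event.* Under the Operating Room rule it produces a drop.

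**Conclusion.** The point holds as a matter of timing. Allocation precedes surgery on every permitted route, the arm is first used in PACU, and nothing conceals it in between. Its firmest consequence is that a rule removing patients operates after randomisation and before treatment, in the hands of staff who may know the arm. A possible effect on intra-operative care comes second.

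The documents give no basis to size either. The range of 0.8 to 7.5 points rests wholly on assumed drop rates and risks; it shows scale and is not an estimate. A reader might conclude that the team will be told the arm, or that the comparison is already biased. The text supports neither. This is a cheap improvement to the design, not a demonstrated error, and it leaves open-label exposure after PACU as it is.

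**What to change.** Leave consent as it is. In the Randomization section, state that the REDCap allocation is opened at the end of the operation, once the plan's existing operating-room condition is met and just before transfer to PACU. Patients who do not meet it are then never randomised, and the operating team cannot know the arm during surgery. The stratum can be the operation performed.

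If that is unworkable, conceal the arm from the surgical and anaesthesia teams until PACU, and state in the Statistical Analysis section that all randomised patients are analysed. This protects intra-operative care but does not remove the drop after randomisation, so both parts are needed.

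The cost is protocol wording and some logistics. A trained team member must open the allocation after each operation, and an HFOT device must be available for every consented patient. The 82 per arm is unaffected. The 10% withdrawal allowance and the 91 per arm should be restated, because operating-room failures would be losses between consent and randomisation. The plan does not split the 10% by reason, so the sponsor will have to supply that split.

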### Day of Surgery

- If patients missed their preoperative labs and x-rays, the chest x-ray and labs can be drawn in the preoperative area the day of surgery
- The consents for surgery and the study will be completed
  - Subjects are allowed to drop from the study at any time. If they do, they will be treated with COT, which is our current standard of care

### Operating Room

- In the operating room, patients will undergo their surgery per normal operating protocol. No patients will be treated differently because of the study.
- At the end of the procedure all patients requiring tracheostomy will have a size 8-0 cuffed Portex trach placed, the cuff will be deflated within 3 hours of leaving the operating room. Total laryngectomy patients will have a laryngectomy tube placed at end of procedure.
- The Anesthesia team will be instructed to treat the patients according to their normal standard of care for head and neck surgery
- All patients must be extubated prior to leaving the operating room, or else they will be dropped from the study
- Subjects will leave the operating room and be transported to the post anesthesia care unit for appropriate monitoring prior to being transferred to a progressive floor
- Starting at the PACU, tracheostomy patients will be started on COT or HFOT via tracheostomy adapter , until occlusive capping of the tracheostomy is tolerated. Once the trach is capped, patients can be placed on oxygen via nasal cannula if it is required to maintain O2 saturation levels as stated below.. Total laryngectomy patients will remain on COT or HFOT via trach mask adapter from the time they are in PACU until the time they can tolerate HME (heat moisture exchange) use or are discharged from the hospital, whichever comes first.

#### Hospital Care

- Care of patients will follow the University of Florida Jacksonville's standardized head and neck protocol (**Figure 1**)
- Analgesia management will be standardized:
  - Scheduled
    - Ibuprofen 600 mg q6 hours scheduled for 72 hours
    - Acetaminophen 650 mg q6 hours scheduled
    - Methocarbamol (Robaxin): 500 mg q 8 hours scheduled
    - Gabapentin 300 mg TID--can scale up if needed to 600 TID after 2 days
  - PRN
    - Oxycodone 5-10 mg q4-6 hours PRN
  - Breakthrough/PRN:
    - Morphine 1-4 mg IV q 2-4 hours PRN
    - Hydromorphone 0.5-1 mg IV q 2-4 hours PRN

NCT05362526

IRB202102700

9/22/22

- Fluids will be standardized to prevent fluid overload/pulmonary edema, and ordered based on body weight, and ideal body weight for obese patients. Fluids will be discontinued once the patient is taking adequate intake by mouth or via tube feeds
- Weaning of the tracheostomy will be standardized
  - If patient is deemed clinically acceptable by team (no sign of pulmonary complication as defined above), the tracheostomy will be downsized on postoperative day 4, to a 6-0 fenestrated uncuffed Shiley, and will undergo occlusive capping as soon as tolerated after the downsize
  - Once the patient tolerates 24-hour capping, and deemed clinically acceptable for decannulation, the tracheostomy will be removed
  - Tracheostomy may be determined necessary if capping not tolerated, or needed for aggressive pulmonary toileting
- Consultation for specialty management of subject comorbidities will be permitted

#### Clinic Follow Up Appointments

- Subjects will follow up in clinic between 1-2 weeks postoperatively from their discharge date
- Vitals and physical exam will be performed, and all subjects will be monitored for adverse events
- Subjects will be closely followed every 1-3 weeks for the first 2 months after surgery
- At 12 days postoperatively all subjects will be called or evaluated in clinic for the final screening for adverse events or pulmonary complications

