#### **Potential adverse events that could result in subject withdrawal from the trial:**

- Subjects unable to be extubated in the operating room after surgery
- Subjects who cannot tolerate COT or HFOT for the specified amount of time each day
- Subjects with surgical complications requiring significant alteration of the treatment plan
  - Subjects requiring a return to the operating room during their admission will be excluded, unless it is for a procedure not related to the original surgery

NCT05362526

IRB202102700

9/22/22

occurring after post op day 3, such as a gastrostomy tube or long-term IV access.

- Subjects who do not stay in the hospital for at least 4 days after surgery

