## **Outcome Measures**

- Primary
  - **Incidence of post-operative pulmonary complication within 14 days after surgery**
    - Postoperative pulmonary complication will be defined as
      - Atelectasis or infiltrate diagnosed by radiologist on any postoperative chest radiograph within first 14 days or discharge (whichever occurs first)
      - Pneumonia
        - *Diagnosis is suggested by a history of cough, dyspnea, pleuritic pain, or acute functional or cognitive decline, with abnormal vital signs (e.g., fever, tachycardia) and lung examination findings. Diagnosis should be confirmed by chest radiography or ultrasonography.* [15]
    - Chronic pulmonary obstructive disease exacerbation
      - *An event in the natural course of the disease characterized by a change in the patient's baseline dyspnea, cough, and/or sputum and beyond normal day-to-day variations, that is acute in onset and may warrant a change in regular medication in a patient with underlying COPD* [16]
    - Adult respiratory distress syndrome (Berlin definition)
    - Need for reintubation/mechanical ventilation
    - Need for non-invasive mechanical ventilation
  - Secondary
    - **Time to tracheostomy decannulation** (half days)

NCT05362526

IRB202102700

9/22/22

- **Hospital length of stay after surgery** (half days)
- **Need for antibiotics for pulmonary complication** (escalation to broad spectrum, addition of a second antibiotic, antibiotics past post-operative day 7)
- **Need for pulmonary physiotherapy** (acapella, flutter, etc.)
- **Discharge destination:** Home vs nursing facility vs rehabilitation

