## **Statistical Analysis**

### Sample Size Rationale

A sample size of 164 patients, 82 in each arm, is sufficient to detect a clinically important difference of 20% in the proportion of postoperative pulmonary complications between arms using a two-tailed z-test of proportions with 90% power and a 5% level of significance. This 20% difference represents 10% of postoperative pulmonary complications using HFOT and 30% of postoperative pulmonary complications in the control arm. Assuming a 10% rate of withdrawal, we will need to recruit 91 patients per arm to be adequately powered to detect the difference.

An interim analysis of the proportion of postoperative pulmonary complications is planned after 100 subjects (50:50) are enrolled to assess whether there will be overwhelming evidence of a benefit from HFOT, as compared with conventional oxygen therapy, or of harm in any study group. As a consequence, the p-value for the primary comparison between the two arms will be adjusted to conserve an overall significance level of 0.05[17]. Descriptive summaries will be frequencies and percentages for categorical variables and means, standard deviations, medians, and quartiles for continuous variables. The primary analysis will compare the difference in the proportion of postoperative pulmonary complications

between the intervention group and the control group. This difference is assessed using univariate analyses and ANCOVA (Analysis of Covariance) models. Demographic and baseline characteristics between groups are assessed using the non-parametric Wilcoxon Rank-Sum test for continuous data, and Pearson Chi-squared test or Fisher's Exact test (when expected frequencies are small) for categorical data. The secondary outcomes will be analyses using the same statistical methods, based upon the data distributions. Data analyses will be performed by a statistician with the Center for Data Solutions.

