### **Possible Discomfort and Risks**

- Participants may be in some discomfort due to their planned head and neck surgery. Patients in this study will be receiving our current standard of care (COT) or HFOT therapy, which is also an established standard of care modality. Thus, risks to patients are low, and have not been observed in similar studies.

There is the minimal risk of a participant's privacy being compromised. Several measures to ensure the privacy protection of those enrolled in the study will be in place as described in the Patient Privacy and Protection section on page 11.

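### Adverse events are monitored, but no safety outcome or by-arm comparison is planned, the interim harm look uses only pulmonary complications, and patients with surgical or device problems can leave the analysis

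*Combined protocol and SAP*

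**What the plan says.** All places are in the combined protocol and SAP.

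- **Collection.** Clinic Follow Up Appointments states that "all subjects will be monitored for adverse events". It adds: "At 12 days postoperatively all subjects will be called or evaluated in clinic for the final screening for adverse events or pulmonary complications". Adverse events and pulmonary complications are thus named as separate things. The Data Safety Monitoring Board section has the investigator monitor events and report them to the IRB. It describes no review by arm.
- **Outcomes.** The primary outcome is "Incidence of post-operative pulmonary complication within 14 days after surgery", a composite of pulmonary diagnoses and ventilatory support. The secondary outcomes are decannulation time, length of stay, antibiotics for a pulmonary cause, physiotherapy and discharge destination.
- **Analysis.** Statistical Analysis covers the primary outcome, baseline characteristics and the secondary outcomes. Adverse events are not mentioned, and no analysis population is named.
- **Interim look.** "An interim analysis of the proportion of postoperative pulmonary complications is planned after 100 subjects (50:50) are enrolled". The same sentence gives overwhelming benefit, or harm in either group, as its purpose. No second variable is given.
- **Leaving the trial.** The section on adverse events that could result in withdrawal lists "Subjects with surgical complications requiring significant alteration of the treatment plan" and inability to tolerate the assigned oxygen therapy. A return to the operating room leads to exclusion, except for certain unrelated later procedures.
- **Risk statement.** Possible Discomfort and Risks concludes: "Thus, risks to patients are low, and have not been observed in similar studies".

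**The concern.** The plan has the pieces of a safety evaluation but does not join them. Events are looked for, but no section says which ones count, how they are compared, or in whom. The one formal look for harm is restricted to the outcome that HFOT is expected to improve.

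The withdrawal rules make this more than missing detail. Return to the operating room, a major surgical complication and intolerance of the device are where non-pulmonary harm would most likely be seen, and each is treated as a way out of the trial. If these events differed between arms, the difference would not be tabulated, and the pulmonary comparison would be made in a group selected after randomisation.

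The question is fair on the protocol's own account. Every patient has a neck dissection, HFOT runs at 60 L/min and is said to deliver positive airway pressure, and Background calls its use after this surgery generally unexplored. Background also says of conventional humidification: "Ultimately, this can cause serious complications like mucous plugging and pneumonia". Pneumonia is in the primary outcome and mucous plugging is not named, so a safety table could also show a benefit of HFOT that the plan does not capture directly.

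**Working it through.** **1. The sections side by side**

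| Event | Where the plan mentions it | Compared by arm? |
|---|---|---|
| Return to the operating room | Withdrawal section (exclusion, with an exception) | No |
| Major surgical complication | Withdrawal section (possible withdrawal) | No |
| Device intolerance | Withdrawal section (possible withdrawal) | No |
| Mucous plugging | Background only | Only if it shows as a component of the composite |
| Reintubation or ventilation | Primary composite | Yes, merged with the other components |
| Slow decannulation, long stay | Secondary outcomes | Yes, without identifying a cause |
| Any other adverse event | Follow-up and monitoring sections | No |

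**2. The plan's own figure.** Inputs from Sample Size Rationale: 10% v 30%, two-sided 5%, 90% power. With a mean proportion of 0.20:

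n = [1.960 × √(2 × 0.20 × 0.80) + 1.282 × √(0.10 × 0.90 + 0.30 × 0.70)]² / 0.20² = (1.109 + 0.702)² / 0.04 ≈ 82 per arm.

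The stated 82 reproduces (power 90.0%). It concerns the pulmonary composite only, and no stated figure bears on safety.

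**3. What 82 per arm can say about harm.** The documents give no adverse-event rates, so every rate here is assumed.

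- Harm of 5% v 1%: expected counts are 82 × 0.05 = 4.1 and 82 × 0.01 = 0.8. Power at two-sided 5% by Fisher's exact test, which the plan names for small expected frequencies, is about 12% (summed over all pairs of binomial counts). The normal approximation gives Φ[(0.04 − 1.960 × 0.0266) / 0.0265] = Φ(−0.46) ≈ 32%, but it is unreliable with counts this low. Power is poor on either figure.
- An observed 4 v 1: the difference is 3/82 = 3.7 points, 95% CI about −2.5 to 10.7 (Newcombe), Fisher p = 0.37.
- A doubling from a control rate of 1%, 2%, 5% or 10%: power about 8%, 11%, 23% or 43% (normal approximation).
- 95% CI half-width at 5% v 10%: 1.96 × √(0.05 × 0.95/82 + 0.10 × 0.90/82) = 8.0 points.
- Zero events: the one-sided 95% upper limit is 1 − 0.05^(1/82) = 3.6%. At the interim, with 50 per arm, it is 1 − 0.05^(1/50) = 5.8%.

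**4. What withdrawal can hide.** The plan allows for 10% withdrawal and recruits 91 to keep 82, so it expects about 91 − 82 = 9 patients per arm to leave. At the assumed 5% v 1%, the expected events among 91 are 91 × 0.05 = 4.6 and 91 × 0.01 = 0.9. All of them could fall within the expected withdrawals, and a table restricted to completers could then show none.

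**The case against.** The case on the other side has substance.

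- **A reader might infer that non-pulmonary harm cannot appear in the results at all.** The documents do not support that. Severe airway harm can enter the primary outcome as reintubation or ventilation. Mucous plugging can enter if it shows as atelectasis, infiltrate or pneumonia. "Time to tracheostomy decannulation", length of stay and discharge destination are compared by arm and can shift. These signals are indirect and do not identify the cause, but they exist.
- **Nor would harm go unrecorded.** Events are monitored, screened at day 12 and reported to the IRB. What is missing is the definition and the comparison.
- **A reader might take the low-risk statement to rest on the one 20-patient study in this population.** The text refers to similar studies in the plural and to established use, and Background also cites a meta-analysis in other major surgery. Nor can an upper bound on harm be derived from the small study, because the protocol reports neither its arm sizes nor its event counts.
- **The interim variable is a legitimate harm signal.** An excess of pulmonary complications in either arm is harm. The gap is that no other kind of harm is reviewed.
- **The harms are not documented.** No section says that HFOT causes wound, flap or air-leak problems. The point asks only that such events be countable.
- **A table would have little power.** This is correct and should be stated in the plan.

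None of this supplies a by-arm safety comparison or keeps the withdrawn patients in view.

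**Conclusion.** The point holds as a recommended change. The plan monitors adverse events without defining safety outcomes or comparing them by arm, its interim harm look covers pulmonary complications only, and its withdrawal rules can remove the patients most likely to show other harm. That such harm is invisible, or that HFOT is known to cause it, does not follow from the documents.

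In size, the gain is in estimation. At 82 per arm the trial could show that an event with no occurrences has a rate below 3.6% (one-sided 95% limit), but it has only about 12% power for an assumed 5% v 1% difference. This rests on assumed event rates, and on reading exclusion and withdrawal as possible loss from the analysis, since the plan names no analysis population.

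**What to change.** 1. In Outcome Measures, add a short set of safety outcomes: return to the operating room, wound or flap complication, air leak, tube obstruction or displacement, and stopping the device for intolerance.
2. In Statistical Analysis, tabulate these, all other adverse events, and withdrawals with reasons by randomised arm, with risk differences and 95% confidence intervals, at the interim look and at the end. Name this table as part of what the harm look reviews.
3. Include all randomised patients, also those withdrawn or excluded, where their data may still be used. Run the table through the day-12 screen, or to day 14 from chart and clinic records. The last contact planned for every patient specifically to screen for events is at day 12, so state which window applies.
4. State that the table is descriptive and that the sample size was not set for it.

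The cost is a few REDCap fields, one table and continued chart follow-up of withdrawn patients. That follow-up is the real extra work. The sample size, the study procedures and the clinical care of patients do not change.
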